cholinesterase inhibitors and/or memantine throughout the duration of the study. Any changes to the medication will be documented in the participant research chart. Medications given for other medical reasons, e.g., antidiabetic or anti-hypertensive medications, will not be altered for the purposes of this trial and the patient's primary physician may adjust such medications as medically indicated throughout the trial. Psychotropic and other medications are allowed. Details of concomitant medication use will be documented at all visits and will be available for statistical analysis.	
7. Either PET amyloid scan positivity or prior CSF biomarker positive for AD (A β 42 and tau/p- tau).	Medical Records or through completing a PET Scan as part of screen
8. A family member, friend, or other individual who is in contact with the patient agrees to serve as the patient's informant during the study and signs the "Informant Information Sheet."	Patient Designation
Exclusion:	
1. Current clinical diagnosis of schizophrenia, schizoaffective disorder, other psychosis, bipolar disorder or current major depression by DSM-5 criteria. Prior history of major depression will not be exclusionary (25% of older adults have a lifetime history of major depression).	Physician Evaluation
2. Active suicidal intent or plan.	Physician Evaluation with SRMP Assessment
3. Current or recent (past 6 months) alcohol or substance use disorder (DSM-5 criteria).	Physician Evaluation
4. Current diagnosis of other major neurological disorders, including Parkinson's disease, multiple sclerosis, CNS infection, Huntington's disease, and amyotrophic lateral sclerosis.	Physician Evaluation
5. Clinical stroke with residual clinical deficits. MRI findings of cerebrovascular disease (small infarcts, lacunes, periventricular disease) in the absence of clinical stroke with residual neurological deficits will not lead to exclusion.	Physician Evaluation
6. Acute, severe, unstable medical illness. For cancer,	Physician Evaluation

patients with active illness or metastases in the last 12 months will be excluded, but past history of successfully treated cancer will not lead to exclusion.	
7. Sitting blood pressure > 160/100 mm Hg.	Physician Evaluation
8. Renal failure as determined by an estimated Glomerular Filtration Rate (GFR) < 44 ml/min/1.73m ² (see 4.3.b.).	Laboratory Report
9. Serum vitamin B12 levels below the normal range.	Laboratory Report
10. Patients with thyroid stimulating hormone (TSH) levels above 4.94 mIU/L.	Laboratory Report
11. Use of benzodiazepines in lorazepam equivalent doses equal to or greater than 2 mg daily.	Patient Report
12. For MRI, metal implants and pacemaker, and claustrophobia such that the patient refuses MRI. In our experience, these exclusions occur in less than 5% of patients with mild AD. MRI is required.	Patient Report
13. Radiation exposure in the prior 12 months that, together with 18F-- Florbetapir will be above the FDA annual radiation exposure threshold. This will be determined through study staff (i.e. Principal Investigator, Study Physician) discussion with potential subjects at Screening, documenting inquiry about radiation history. If there is any history of additional radiation exposure in the past year; it will be reviewed with PET Center staff.	Patient Report and Physician Evaluation
14. Severe vision or hearing impairment that would prevent the participant from performing the psychometric tests accurately. This will be a clinical determination by the study physician without formal testing or audiometry.	Physician Evaluation

Consent Procedures

Explain, in this section:

Explain the consent procedures for this protocol.

Voluntary written informed consent will be obtained from all subjects and their informants by Drs. [name], [name], [name], and/or [name].

All patients at enrollment will be assessed for capacity to consent and this will be documented in the chart.

The Consent Form describes the nature of the procedures and time requirements, potential risks, the confidentiality of information, and the rights of research participants, including their right to withdraw from the research at any time without loss of benefits to which they are otherwise entitled. It is made explicit that this protocol involves randomized, double-blinded treatment with valacyclovir or placebo with return visits at specified time points, with a description of the research assessments. The consent process also includes documentation of permission to obtain previous medical records.

The IRB-approved forms for Informed Consent and Assessment of Capacity are made part of the patient's permanent medical record and a copy is filed in the participant's research chart.

The study physician obtaining consent signs a Consent Procedure Note, documenting that research procedures and consent forms have been discussed with the patient, the patient understands what is required of them, and would like to participate in the study.

The Consent Procedure Note has been expanded for the Study Physician to indicate whether or not the participant agreed to the storage of biological samples and future use of such data.

Specific consent issues and risks pertaining to apolipoprotein E genotyping are described in the sections below.

If the eligibility screening for this study is conducted under a different IRB protocol, enter the NYSPI IRB# N/A.

Waiver of Consent / Authorization

The following sections are to be completed for the appropriate waiver/alteration of consent.

Waiver of Consent for use of Protected Health Information (PHI)

What records do you wish to review?

What information are you seeking access to?

Describe your plan to protect identifiers from improper use and disclosure.

Describe your plan to destroy the identifiers as soon as possible, consistent with the conduct of the research, or provide a health or research justification for retaining the identifiers or explain how retention is required by law.

Explain why the research could not be practicably carried out without the information (for which you are requesting access).

Explain why the research cannot be practicably carried out without the waiver.

Explain how/if subjects will be provided with additional pertinent information after participation.

Justification for Waiver or Alteration of Consent

Waiver of consent is requested for the following.

Explain why your research cannot be practicably carried out without the waiver or alteration.

Describe whether and how subjects will be provided with additional pertinent information after participation.

Waiver of Documentation of Consent

Would the consent form signature be the only link between the subject's identity and the research data?

Is breach of confidentiality the main study risk?

Is consent for this research procedure ordinarily not required outside of the research context? Explain.

Describe the study component(s) for which waiver of documentation is requested.

Waiver of Parental Consent

Explain why parental/guardian consent is not a reasonable requirement to protect the minor participants in this study.

If parental consent is waived, describe a mechanism that will be substituted to provide appropriate protections for the subjects.

Assent Procedures

In this section, please describe the procedures by which subject assent will be assessed and / or recorded.

Participants who respond to outside advertising will complete a telephone screen prior to completing a screening visit in the clinic.

Participants referred to the study will undergo a screening process (MMSE) and initial check for inclusion/exclusion criteria (previous positive AD biomarkers via 18F-Florbetapir Amyloid PET or CSF studies; diagnosis of MCI by ADNI criteria described in formal Inclusion Criteria). If the patient appears eligible based on screening, a study physician will confirm by patient interview

that all inclusion/exclusion criteria are met, and they will go over the details of the study with the patient as described in the informed consent form.

Patients will be given ample time to review the consent forms and will be given the opportunity to ask questions. Patients will sign the official study informed consent and HIPAA Authorization at Screening. The Consent Form Summary will also be presented to the patient at Screening, but doesn't require signature.

Patients with MCI are expected to be able to consent for themselves and surrogate and/or informant consent are not required.

The individual obtaining consent will explain that if travel does not seem safe, the study visit(s) can be rescheduled.

At Screening, Principal Investigator and/or Study Physician will review prior radiation exposure with potential subjects. This information will be reviewed with PET Center staff for their approval before proceeding with recruitment. Only Drs. [name], [name], [name] and [name] will obtain consent from participants.

Informants: In our prior studies, 92% of patients had at least one informant available for interview. Most informants provided information by telephone interview. In the proposed study, we will use this approach for informants who cannot accompany the patient to visits. Informants will be asked questions regarding the participant's social and everyday functioning, as well as questions regarding the participant's memory. These involve standardized rating scales as described in further sections of the PSF. Research coordinators will obtain written informed consent from the informant to provide this information during the study using the "Informant Information Sheet" attached to the participant consent form. Informants will solely be interviewed to provide information about study participants, and will not be providing any information about themselves beyond basic contact information.

The IRB-approved forms for informed consent and for assessment of capacity are made part of the patient's permanent medical record, with a copy being filed in the research chart.

Throughout the study, the study physicians will cross-cover each other for patient assessments and management in the study. All study physicians are board certified psychiatrists and their clinical role is to serve as the study physicians.

Memory Disorders Clinic: Memory Disorders Clinic study physicians, who work in a supervisory capacity or follow patients whom they have seen for a long period of time. New evaluations are conducted by Neurology fellows. If a patient is potentially eligible, these fellows will briefly describe the study and if the patient is interested then refer the patient to Drs. [name] or [name] or [name] or [name] who will screen and recruit the patient if eligible.

Behavioral Neurology Practice Group: Physicians who are part of the Behavioral Neurology Practice Group evaluate a patient who may be eligible, respective physician will explicitly inform patient that they have the option of getting a second opinion regarding study participation, from a physician in the clinical setting, who is not an investigator in the study and immediately arrange for that second opinion if requested.

Persons Designated to Discuss and Document Consent

Please list all the names of persons designated to obtain consent / assent. All persons must complete CITI training for NYSPI. The PI affirms that each name listed has completed the appropriate training.

[name], MD

[name], MD

[name], MD

[name], MD

Independent Assessment of Capacity

*This section is designated for those studies that have been identified where subjects **May Lack** capacity to consent.*

Describe the Methods/procedures for capacity assessment. Patients with amnesic MCI (eMCI or IMCI) with Folstein MMSE score greater than or equal to 23/30 at screening will sign consent to participate in the protocol, and all patients will be required to have the capacity to consent to enroll in the protocol. All informants will be required to sign the "Informant Information Sheet" to indicate that they agree to the responsibilities detailed in the document. The study lasts 12 months (52 weeks) or one year, for each participant.

If your study involves subjects who **DO LACK** capacity to consent, please justify. All patients are required to have the capacity to consent at their screening visit, as this is consistent with a diagnosis of MCI.

The following approach will be used during the 12-month trial. If the Folstein MMSE declines to below 18 out of 30 at any time-point during the trial, an independent assessment of capacity will be conducted. If the independent assessor determines that the patient retains the capacity to participate in the study, the patient will continue in the study. If the patient no longer retains the capacity to consent in the study, then the patient will be asked to assent to continued participation and to also agree that the surrogate designated by the patient will continue to act in this capacity. If both these criteria are met, the patient will continue in the study. If both these criteria are not met, the patient will be withdrawn from the protocol.

Procedures for surrogate consent. For NYSPI/Columbia, New York State regulations regarding capacity to consent, as utilized by the New York State Psychiatric Institute IRB, will be followed. Under no circumstance will a patient objecting to participation be included in the study.

1. A psychiatrist or licensed clinical psychologist who is independent of the research must confirm that the patient still retains the capacity to designate a surrogate, i.e., identify the surrogate and indicate that the surrogate can consent on the patient's behalf for the research study. **[name]** will be the independent evaluator for this study. She will follow the procedures described below, using the PCS forms attached, as an addendum to the Informed Consent Form.
2. The document designating the research surrogate must be witnessed by two persons who are independent of the research. The psychiatrist or licensed clinical psychologist who assesses the patient's capacity to choose a surrogate may also be witness to the choice of the surrogate.
3. If the patient chooses a surrogate but is unable to sign the document, another person may sign for the patient and the two witnesses shall, in writing, confirm the patient's choice of a surrogate and witness the signature of the person signing for the patient.
4. The surrogate cannot function as a witness to the choice of the surrogate. A family member or friend of the patient who is not the surrogate may function as a witness.

5. The surrogate cannot be an administrator or employee of the facility at which the research is conducted or the facility conducting the research. This restriction does not apply if the person is related to the patient by blood, marriage, or adoption. The selection of a patient's spouse as a surrogate is revoked upon the legal separation or divorce of the patient and spouse unless the patient specifies otherwise.
6. Notice of the appointment of a surrogate must be provided to the Mental Health Legal Service (MHLS). We will inform MHLS each time a patient who lacks capacity to consent and appoints a surrogate is recruited for this protocol.

Study Procedures

Provide a clear, concise narrative of study procedures with special attention to the subjects' involvement. Detail the overall study timeline and location of study procedures, list all interventions, assessments and interviews, estimate the duration of each procedure, provide dosing schedules, identify study personnel involved in each procedure, and provide credentials for relevant personnel. If treatment is provided, specify the minimum credentials for providing that treatment. For complicated study designs, we strongly encourage attaching tables, flow-charts, and study algorithms.

Columbia University Medical Center/New York State Psychiatric Institute

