AD-biomarker positive adults (male and female), diagnosed with amnesic MCI (eMCI or IMCI) who test positive for serum antibodies to Herpes Simplex Virus (HSV1) or Herpes Simplex Virus (HSV2).	50 AD-biomarker positive adults with amnesic MCI (eMCI or IMCI) who test positive for serum antibodies to HSV1 or HSV2.	56 AD-biomarker positive adults with amnesic MCI (eMCI or IMCI) who test positive for serum antibodies to HSV1 or HSV2.	50-95.

Gender, Racial, and Ethnic Breakdown:

No minority group is excluded from research participation. Based on our current clinic distributions at NYSPI, 65% are expected to be Non-Hispanic White, 15% Hispanic, 15% African American, and 5% Asian. This is the expected representation in the proposed study. Based on our experience in our clinics, women will constitute 60% and men will constitute 40% of subjects.

Suicide Risk Management Plan

This section will include all information regarding the Suicide Risk Management Plan.

Always ask questions 1 and 2.	Past Month
1) Have you wished you were dead or wished you could go to sleep and not wake up?	
2) Have you actually had any thoughts about killing yourself?	
If YES to 2, ask questions 3, 4, 5 and 6. If NO to 2, skip to question 6.	
3) Have you been thinking about how you might do this?	
4) Have you had these thoughts and had some intention of acting on them?	High Risk
5) Have you started to work out or worked out the details of how to kill yourself? Did you intend to carry out this plan?	High Risk
Always Ask Question 6	Life-time Past 3 Months
6) Have you done anything, started to do anything, or prepared to do anything to end your life? <small>Examples: Collected pills, obtained a gun, gave away valuables, wrote a will or suicide note, held a gun but changed your mind, cut yourself, tried to hang yourself, etc.</small>	High Risk

Any **YES** indicates that someone should seek behavioral healthcare.
However, if the answer to 4, 5 or 6 is **YES**, get **immediate help: Call or text 988, call 911 or go to the emergency room. STAY WITH THEM** until they can be evaluated.

Download
Columbia
Protocol
app

ANTI-VIRAL THERAPY IN MILD COGNITIVE IMPAIRMENT

Patient ID: Patient Initials: Date: Rater Initials:

Intervals: Screen, Baseline, Week 2, **Week 4**, Week 12, Week 26, Week 52

Suicide Risk Assessment

*Always ask questions 1 and 2.

1.) Since we last spoke, have you felt as though you wished you were dead?

Yes No

2.) Have you had any actual thoughts about killing yourself?

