Yes No

If YES to 2, ask questions 3, 4, 5, and 6. If NO to 2, skip to question 6.

3.) Have you been thinking about how you might do this?

Yes No

4.) Have you had these thoughts and had some intention of acting on them?

Yes No

5.) Have you started to work out or worked out the details of how to kill yourself? Did you intend to carry out this plan?

Yes No

*Always ask question 6

6.) Have you done anything, started to do anything, or prepared to do anything to end your life?

Yes No

Any YES indicates that someone should seek behavioral healthcare.
However, if the answer to 4, 5, or 6 is YES, get **immediate help: Call or text 988, call 911, or go to the emergency room. STAY WITH THEM** until they can be evaluated.

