The study physician will administer the assessment at all appointments. If the patient has a positive response characterized as “High Risk” as per the table, the study physician will take the appropriate clinical action, such as taking the patient to the emergency room, admitting the patient, or deciding to monitor them more closely. To maintain and improve patient safety, we are now formalizing the administration of the Columbia Suicide Severity Rating Scale (C-SSRS), an assessment used in Columbia University Irving Medical Center psychiatry clinical facilities including the Emergency Room. This will be documented in the patient’s chart. If responses to questions 1 and 2 in the 6-item scale are “no”, the rater skips to question 6. If the answer is “yes” to question 2, questions 3-6 are asked. Any “yes” on the scale indicates that someone should seek behavioral healthcare and the research team will ensure that this occurs. Further, if the answer to any of the items of 4, 5, 6 is “yes”, immediate action will be taken by the study physician, which involve the patient being taken to the Emergency Room or calling 911. This will be documented in the patient’s chart and an SAE will be submitted to the IRB. Based on the clinical situation, the study physician will decide, in conjunction with the study PI ([name]), if this should be reported as a Serious Adverse Event to the IRB, e.g., if the patient is hospitalized for suicidality. If the patient is hospitalized, the patient will be told to interrupt the study treatment, valacyclovir or placebo. Of note, there is no evidence that valacyclovir use is associated with increased suicidal ideation. If treatment interruption occurs, treatment with study medication can be resumed within 6 weeks (as per the protocol) if the patient no longer is deemed to be high risk for suicide based on repeat administration of the same suicide assessment that is used at CUIMC facilities. Non-clinical staff (e.g. research assistants) may become aware of suicide risk via routine phone calls and visits with the patient. If a non-clinical staff member is made aware of suicide risk they are required to immediately report suicide risk to the study physician available. There is a rotation for a study physician on call, which is constant each week, and when the study physician is not in, this authority is automatically delegated to [name] who is available 24/7. If the non-clinical staff member is made aware of the suicide risk outside of MDC clinic hours, they are required to report the suicide risk to [name], who is available for contact at all times (i.e., 24 hours/day, 7days/week). When [name] is not available he

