2. Arrangements for Clinical Coverage (CC)		Study physicians administer the C-SSRS and they will take clinical action themselves, consulting the PI if needed.
2A. Will research assistants be administering the C-SSRS? If yes, go to 2B		No, only study physicians will administer the C-SSRS.
2B. How they will call in CC		N/A
3. Standards for Clinical Evaluation and Risk Mitigation	Describe	Study physicians administer the C-SSRS and they will take clinical action themselves, consulting the PI if needed.
4. Emergency Contacts	Requested or Required	Required.
5. Indicators for Review for Possible Discontinuation	Operationalize in terms of scores on C-SSRS	A C-SSRS score of 4 or higher at any time will lead to review for discontinuation by the study physician in consultation with the PI and review by the Independent Clinical Monitor.

6. Indications for Independent Clinical Monitor	Describe indications	When a participant's C-SSRS score of 4 has prompted a team review for possible discontinuation, an independent clinical monitor (Psychiatrist) will assess the patient and review with the PI if study discontinuation is warranted.
7. Standards for Documentation of CC		
In the research chart, if the C-SSRS threshold criteria are triggered, the study physician who administered the C-SSRS will describe the reason for which the clinical review was activated and what efforts were made by the study physician (with the assistance of the research team) to secure the participant's safety. The note will contain a description of the evaluation including pertinent details of the history obtained, a mental status exam, and description of the assessment of risk and clinical rationale. The note will include the referral process (active or passive) and intent to follow-up.
 
Follow-up should be confirmed in a subsequent note within 72 hours. If the participant has received clinical care from the research team during the study, the evaluation, referrals made, and follow-up also need to be documented in the clinical chart.

8. Standards for reporting AEs and SAEs		Any ER visit for suicidal behavior must be reported as an SAE; any suicide attempt must be reported as an SAE even if it did not result in an ER or doctor visit; a suicide death is an SAE. Further, if the answer to any of the C-SSRS items of 4, 5, 6 is "yes", immediate action will be taken by the study physician, which involve the patient

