- 3.) Based on the result of a blood draw at the week 12 visit, if the serum creatinine level increases to be greater than 1.5 mg/dl, or eGFR declines to less than 44 mL/min, we will lower the study medication to the minimum dose of 2 g valacyclovir or placebo per day. Patients will then have blood collected and labs repeated at an additional visit, at week 16. If, at week 16, kidney function is still abnormal based on the above criteria, study medication will be discontinued for this patient. The reduction in kidney function will be communicated to the patient's primary care physician.
- 4.) The patient will be discontinued if 1) the CIBIC-PLUS score is higher than 80 (consistent with moderate dementia or moderate to severe behavioral changes), or if 2) the C-SSRS score is 6 or higher on the Suicidal Ideation Subscale, or if there is any positive score on the Suicidal Behavior Subscale or Behavior Lethality Subscale.

If MRI Acquisition must be terminated for some reason, the patient can still continue in the protocol. This is because MRI outcomes are secondary and not primary.

This is an intent-to treat protocol. Therefore, a patient who is discontinued early in the study due to the above reasons will be followed and evaluated (whenever feasible) until the Week 52 visit, or until the patient withdraws his/her consent to participate.

Blood and other Biological Samples

Describe how the sample will be used and indicate, when relevant, the amount of the sample. The IRB wants to know that the sample is sufficient for the purposes of the study, but that sampling is limited to what is minimally necessary.

If you've indicated that you intend to store a sample for future use, indicate where the sample will be stored, how long the sample will be stored, and to what purposes the sample will eventually be put. Check the IRB website at <https://irb.nyspi.org/investigators/guidance/genetic-research> for specific guidance and additional information about future use of DNA samples.

Protocol Summary Form

Routine Laboratory Tests: At Screening, Weeks 12, 26 and 52, blood will be collected for the following screening laboratory tests, which will be performed by the OMH Clinical Laboratories-Nathan Kline Institute: CBC, BUN, creatinine, eGFR, electrolytes, liver and thyroid function studies, B-12, and folate (a total of 20 mL blood will be collected across all four timepoints).

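### The mandatory suicidality stop cannot be scored from the 6-item C-SSRS in use, and the restart, review and emergency wording does not line up with it

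*Protocol*

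**What the plan says.** Four parts of the protocol deal with suicidality during the study.

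- **Criteria for Early Discontinuation, item 4.** The patient is to be discontinued, with no discretion, if "the C-SSRS score is 6 or higher on the Suicidal Ideation Subscale". A second trigger applies "if there is any positive score on the Suicidal Behavior Subscale or Behavior Lethality Subscale". Under the intent-to-treat rule in the same section, a patient stopped early "will be followed and evaluated (whenever feasible) until the Week 52 visit".
- **Suicide Risk Management Plan, narrative.** A patient hospitalized for suicidality interrupts study drug. After that, "treatment with study medication can be resumed within 6 weeks (as per the protocol) if the patient no longer is deemed to be high risk", judged by repeating the suicide assessment used at the medical center. For a High Risk answer, the narrative first lists emergency room, admission or closer monitoring as examples of suitable action. It then requires the emergency room or 911 for a yes on item 4, 5 or 6.
- **SRMP Checklist, items 5 and 6.** "A C-SSRS score of 4 or higher at any time will lead to review for discontinuation by the study physician". The PI is consulted, and the independent clinical monitor also reviews the case. The monitor "will assess the patient and review with the PI if study discontinuation is warranted".
- **The instrument.** Checklist item 1 confirms the 6-item C-SSRS. Both the C-SSRS table and the study's own Suicide Risk Assessment form have five questions about thoughts, intent and plans (items 1 to 5) and one about acts (item 6: "Have you done anything, started to do anything, or prepared to do anything to end your life"). The table marks items 4, 5 and 6 as High Risk and heads item 6 "Life-time Past 3 Months". The study form gives item 6 no time window.

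**The concern.** A mandatory stop protects participants only if the person completing the form can tell when it has been met. Here the stop is written in subscales that do not appear on the form, with an ideation threshold that the form does not appear able to reach. The plan that physicians will have in hand when an event occurs speaks instead of interruption, possible restart and review, and does not point to the stop.

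Staff following that plan in good faith could review a patient and keep or restart study drug when the discontinuation criteria call for a stop. That would be both a safety problem and a protocol deviation. A physician could also cite the closer-monitoring wording for an answer that the plan elsewhere sends to emergency care.

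**Working it through.** The documents give no figure to reproduce. The check is one small count and a comparison of rules.

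**1. Can the ideation threshold be reached?** The threshold is 6 (Early Discontinuation item 4). The thought questions are items 1 to 5, which makes five. No scoring rule is given, so two simple ones are assumed:
- One point per yes: 5 × 1 = 5, below 6.
- Highest item endorsed among items 1 to 5: 5, below 6.

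A 6 is possible only if item 6 is counted: either all six answers are yes (5 + 1 = 6), or the highest item is item 6. But item 6 asks about acts, and no text places it in an ideation score.

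**2. Can the behaviour criterion be read from the form?** Neither the table nor the study form shows a Suicidal Behavior or Behavior Lethality subscale. Item 6 is plainly about behaviour, and the Assessment Instruments section says the scale covers suicidal behaviour. Treating a yes on item 6 as a positive behaviour score is therefore a short inference, but the protocol does not state it. Nothing on the form grades lethality.

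**3. Trace one event: a suicidal act during the study that leads to admission.**
- Early Discontinuation item 4, if item 6 counts: discontinue.
- Suicide Risk Management Plan narrative: interrupt, with restart possible within 6 weeks. No exception is made for behaviour.
- SRMP Checklist items 5 and 6: review, then a judgement. A score of 4 or higher includes the more serious cases.

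No section says which rule prevails. The narrative's reference to the protocol is attached to the 6-week limit, not to item 4 of the discontinuation criteria.

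**4. Trace a yes on item 4 or 5 without any act.** By step 1 the ideation score is at most 5, so the mandatory stop is not met. Review and restart then conflict with nothing. The conflict in step 3 is confined to behaviour events.

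**5. Emergency response.** The High Risk answers are items 4, 5 and 6. For these the narrative first allows closer monitoring, then requires the emergency room or 911. The stricter sentence appears three times (narrative, checklist item D, checklist item 8), and both forms call for immediate help. The closer-monitoring option appears once.

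**The case against.** The strongest reply is that the rules form two tiers: review from a score of 4, and a mandatory stop for the worst events. Checklist item 10 gives this some support. It says participants should generally be able to continue if their suicidality does not require removal, and that the stated C-SSRS criteria fit that approach. A lower trigger for review does not cancel a higher stop, and permission to resume does not override an instruction to discontinue. This is probably what was meant. However, the tiers are not written down, and the upper one is expressed in scores that the form does not produce.

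A reader might infer that the plan puts patients back on study drug after a suicide attempt. The documents do not support that as the expected course. Restart requires a repeat assessment that is no longer high risk. On the table, item 6 covers lifetime and the past 3 months, which is longer than the 6-week restart limit. On the study form it has no window at all. A recent act would normally still be a yes and block restart, and Early Discontinuation item 2 ends treatment after more than 6 weeks off drug. A restart route opens mainly if the since-last-contact wording of item 1 on the study form is carried over to item 6.

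A reader might also infer that a 3-month look-back misses behaviour between widely spaced visits. No section relies on a 3-month window alone, so that is not a gap in the plan.

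On the emergency response, the closer-monitoring phrase sits in a list of examples and is followed by a more specific, repeated rule. It is most likely leftover wording, which is a reason to delete it.

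The practical consequence is small. Active suicidal intent or plan is an exclusion. The study physician, the PI and an independent psychiatrist all see such cases. The plan states that there is no evidence linking valacyclovir to suicidal ideation.

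**Conclusion.** The point holds in a narrow form. The mandatory stop cannot be applied from the 6-item form as written: the ideation threshold is 6 against a maximum of 5, and the behaviour subscales are not on the form. The maximum of 5 rests on the assumed scoring rules, and reading item 6 as suicidal behaviour is an inference from its wording.

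One restart sentence and two checklist items make no exception for events that meet the stop. This inconsistency is limited to behaviour events. It would seldom lead to an actual restart, but no text resolves it. One closer-monitoring phrase contradicts the emergency rule for the same three items.

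This is a participant-safety clarification worth making, not a threat to the trial's conclusions. A reader might infer bias in the efficacy results. The documents do not support that, because few events are expected and discontinued patients remain in follow-up where feasible.

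**What to change.** 1. **Criteria for Early Discontinuation, item 4.** Restate the stop in terms of the 6-item form. A yes on item 6 for an event during the study is a mandatory stop. Replace the ideation threshold of 6 with one the form can reach, or delete it. Add a line to the Suicide Risk Assessment form recording whether an item 6 event occurred since the last assessment, so that an older lifetime event does not trigger the stop.
2. **Suicide Risk Management Plan narrative (restart) and SRMP Checklist items 5 and 6 (review).** Add an exception: events meeting Early Discontinuation item 4 end study drug without restart.
3. **Suicide Risk Management Plan narrative (High Risk answers).** Delete the closer-monitoring option for items 4 to 6, so that the emergency room or 911 rule governs. Do not add a 3-month limit to that rule: it would loosen protection and contradict both forms.

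The cost is wording in one IRB amendment, including one form line, with no new visits, staff or patients. The downside is that physicians and the monitor lose a little discretion in these few cases.
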